**BACKGROUND**

Mental health concerns for people receiving hemodialysis are disproportionately high and undertreated. Isolation, fear of severe illness and limited access to healthcare services during the COVID-19 pandemic has contributed to an increase in mental health distress. As one patient explained, “*Mental health can deteriorate in a split second and linger long after. If a patient has no one to talk to, it can become worse than the disease.*”

*Triple I: Improving Information, Interactions and Individualization for people receiving in-centre Hemodialysis*, a multi-centre mixed methods Can-SOLVE CKD Network project, identified the Top 10 Challenges to in-centre hemodialysis care. Importantly, we found that people receiving hemodialysis view addressing access to mental health care as a top priority. Specifically, coping with hemodialysis and an individualized, accessible, culturally-sensitive approach were identified as key mental health care gaps. Although potential solutions to these gaps exist, their feasibility and efficacy is unknown.

The prevalence of self-reported mental health symptoms for adults receiving hemodialysis is 2-5 times higher than the general population and associated with adverse outcomes. Despite increasing needs for mental health care due to the additional pressures from the COVID-19 pandemic, current mental health supports for individuals receiving hemodialysis are inadequate. Hemodialysis clinicians acknowledge the gaps in mental health care in hemodialysis need to be addressed, but lack training and resources to provide such care.

As a part of the Can-SOLVE CKD Network of researchers, in which patient engagement is a guiding principle of all the research projects, patient partners form an integral part of our diverse research team and will contribute to each stage of the project. Through our work with the Triple I project we have expertise in authentic patient engagement and have established relationships and collaborations with Indigenous stakeholders. We will use a *gender-based analysis plus* (GBA+) approach that will consider sex, gender, ethnicity, race and age in order to be sensitive to the effect of identity factors on mental health. Such factors can account for differences in the overall burden of mental health, preferences for and response to treatment and willingness and ability to access mental health resources.

Our research approach will ensure the development of individualized, accessible and culturally-sensitive mental health supports and implementation strategies. Specifically, systemic racism and historically-abusive institutional practices have resulted in inter-generational trauma and mistrust of the healthcare system and have directly impacted the health of Indigenous peoples. In an effort to bridge the gaps towards reconciliation, this research aims to make mental health services available, appropriate and accessible, potentially reducing mental health inequities faced by Indigenous individuals receiving HD in Manitoba.

## AIMS

In partnership with people living with kidney disease, clinicians, healthcare providers and decision makers, the overall goal of this program of study is to identify and address priorities for improving mental health care for individuals receiving hemodialysis. By mobilizing research-generated-knowledge from Can-SOLVE 1.0 (Triple I) and engaging patient partners at all stages, from conceptualization to knowledge translation (KT) of results, this project will optimize person-centred mental health care, leading to improvements in mental health, patient experience and quality of care in hemodialysis.

***Aim 1:*** to identify and catalogue the existing mental health resources available to individuals receiving hemodialysis in Canada; including identifying and cataloguing those resources that are specifically targeted to Indigenous individuals receiving hemodialysis in Manitoba.

***Aim 2:*** to identify the top priorities to address in mental health care in hemodialysis and potential innovations (e.g. tools, strategies, models of care) to improve mental health care in people receiving hemodialysis, as identified by multiple stakeholders including, people receiving hemodialysis/caregivers and healthcare providers.

***Aim 3a:*** Using information obtained in the first TWO study aims, we will design an evidence-based mental health support strategy tailored for Canadians receiving hemodialysis, and develop implementation and evaluation plans to test this strategy.

***Aim 3b:*** Implement and evaluate the Alberta pathway for mental health for individuals receiving hemodialysis.

## METHODS

This multicentre, mixed methods project engages patient partners at every stage; from establishing methodology for the environmental scan and qualitative data collection to devising and testing implementation strategies. Our iKT approach follows the Knowledge-to-Action-Framework, working towards research-driven implementation (see Appendix A for Project Framework).

**Aim 1: Environmental scan of mental health resources available for people receiving hemodialysis.**

We will perform a cross-Canada environmental scan to develop a national online inventory of resources for mental health issues. Some resources included may be specific to people receiving hemodialysis, but we will include all resources available to the general population as well. Resources will be identified systematically provincially using online Google/Web search for resources, including health agencies and public-facing resources. Once compiled, the resources will be reviewed by patient partners and other stakeholders (caregivers, healthcare providers) for completeness and to identify key care gaps.

In Manitoba, we will engage with First Nations and Metis organizations, (First Nations Health and Social Secretariat of Manitoba; Ongomiizwin – Indigenous Institute of Health and Healing at University of Manitoba; Manitoba Metis Federation), Indigenous patient partners and healthcare providers and Indigenous knowledge keepers to identify existing culturally-sensitive and appropriate mental health resources for Indigenous people to be included in the environmental scan for Manitoba

The provincial mental health resources collected will be compiled and developed into an online accessible resource housed on the Mind the Gap Project website (<https://www.mindthegap-ckd.ca>) and at <https://www.healthyqol.com/kidney>.

*STATUS: ENVIRONMENTAL SCAN COMPLETED and is being updated regularly. In Manitoba, efforts to engage Indigenous organizations and individuals continue.*

**Aim 2: Identifying priorities in mental health care for people receiving hemodialysis.** This will be a pan-Canadian qualitative descriptive study to provide a descriptive summary of participant's priorities for addressing mental health care gaps for people receiving hemodialysis as well as their reasons for these suggestions and potential solutions to these priorities. Three sequential components of qualitative data collection will be conducted (1) surveys, (2) priority setting process workshop and, (3) focus groups:

**1) SURVEYS: Identifying priorities for mental health care in people receiving hemodialysis.**

Two similar but distinct open-ended surveys (available electronically through REDCap and in paper-based format) will be conducted across Canada with (A) People receiving hemodialysis/their caregivers and (B) healthcare providers working in hemodialysis. A period of 3 months will be given to complete this exercise. The two versions of the survey will consist of open-ended questions and will be completed anonymously. No IP addresses will be stored. In addition, we will request that all survey respondents provide the following information on the last page of the survey: age (10-year groups), province of residence, gender, ethnicity, profession, role (person living with kidney disease or caregiver of patient/relative, health care provider, other) and how long they (or the person with kidney disease they are associated with) have been on hemodialysis/working in hemodialysis. This information is being collected to determine

whether the population of interest has been captured and whether priorities for mental health are influenced by these factors.

*a. People receiving dialysis/caregivers:* We will contact patients and caregivers for participation in 2 ways. First, we will post a link to the survey on the following websites: Canadian Nephrology Trials Network (CNTN), the Kidney Foundation of Canada, Can-SOLVE CKD, and clinical kidney care program websites across the country. Posters will also be placed in hemodialysis unit waiting rooms across the country to make people attending hemodialysis aware of the survey. We plan for the survey to be available online for 3 months.

To allow for individuals who do not have access to the internet or who prefer to complete hard copy surveys, up to 5 hemodialysis centres across Canada will provide hard copy surveys to the people dialyzing in their unit and invite them to complete the questionnaire (either by paper or online). Currently Edmonton, Winnipeg (Seven Oaks Hospital unit; Health Sciences Centre hemodialysis units and St. Boniface Hospital hemodialysis units) and Halifax will participate and 2 more sites will be identified to ensure that in total surveys are geographically representative across Canada. The survey will provide a letter of information on the first page summarizing the project, explaining that the survey is entirely voluntary and that completion indicates consent. An information poster advertising the survey will be posted in the waiting room of participating hemodialysis centres. Hemodialysis clinic staff will distribute copies to people receiving hemodialysis who are eligible for participation during their dialysis sessions and provide an envelope to ensure anonymity when returning surveys. A study research assistant will be present in the hemodialysis unit to assist individuals with survey completion if necessary. Patient partners, who are partners in research and have lived experience either as a hemodialysis patient themselves or as a caregiver for a loved one, will also be present in the hemodialysis unit to discuss the study and survey with patients and answer any questions they may have. For mental health support, the information letter will contain instructions on how to receive such support, including but not limited to (1) requesting for a renal social worker, (2) and providing a link (i.e. <https://healthyqol.com/kidney>) to a website with a catalogue of available mental health resources specific to their province of residence. We aim to recruit 60-80 patients/caregivers including 25% Indigenous patients/caregivers (purposive recruitment) to complete the survey in Winnipeg (Total 300 across the country). Eligible patients will be currently treated with maintenance hemodialysis, be aged 18 years or older, and be able to communicate in English.

*b. Healthcare providers:* We aim to recruit 40-50 healthcare providers from Manitoba with HD expertise (total 200 overall including all sites). A study staff member will distribute an email to participating hemodialysis unit managers which will include a study information letter and a link to the online survey and will ask the managers to forward email to all hemodialysis unit staff. To ensure we capture our population of interest, participants will also be invited using a purposive (supplemented by snowball) sampling approach. Key stakeholders in nephrology from the Manitoba Renal Program will be asked to recommend nephrologists, nurses, allied health professionals and policy makers who have HD expertise to participate in this study. Contact information will be identified from publicly available sources.

**Survey A for people receiving hemodialysis/their caregivers** will be further developed and refined using an iterative process of action and reflection from piloting for face and content validity in collaboration with our Mind the Gap project patient partners. A second pilot will be performed with the first 10 patients who complete the survey in Winnipeg after which survey revision for readability and comprehension may occur.

At the Winnipeg site, the study Indigenous patient partner sees this project as an opportunity to help communicate the importance of being engaged in one's care to both Indigenous and non-Indigenous individuals receiving HD. As such, after the bedside nurses provide each patient with the survey and review the survey letter with the patient, the patient partner (when available) will be present in the unit and offer to discuss the study with people receiving hemodialysis in they feel this may be helpful in understanding the study and survey.

Surveys will be completed anonymously. Hardcopy surveys will be placed in blank envelopes by responders and collected by hemodialysis staff at each hemodialysis unit and picked up by the study coordinator on a weekly basis at each site. Participants may also mail completed surveys to Winnipeg site (stamped, addressed envelope will be provided in this situation).

**Survey B for healthcare providers** will be developed and piloted for face and content validity in collaboration with our Mind the Gap team members. The final survey will be sent by email with a hyperlink to complete the survey online directly into the secure online database.

All survey answers will be entered (either by participant if completed online or by research assistant if paper copy) into a secure, encrypted RED-CAP (Research Electronic Data Capture) database housed/managed at the University of Manitoba Centre for Healthcare Innovation. Access to the database will be granted to one research team member at each study site.

### ***Data Analysis - Surveys***

Quantitative analyses will assess differences (via counts, frequencies and proportion) in the desire for specific mental health care issues or needs to be addressed across participant groups.

Demographic data collected from the survey will be analyzed and reported by frequency in aggregate to describe study participants and to ensure a diverse study sample of the Canadian in-centre HD population. In addition, subgroup analyses in terms of differences in priority by occupation, age, gender, ethnicity, and geographic region will also be performed.

Answers to free text questions will be collated using NVivo Version 12 and reviewed for common themes and codes. Data analysis will occur at the Winnipeg study site. Themes from the different participant groups (patients/caregivers and providers) will be compared and contrasted.

In the reporting, perspectives relating to mental health care challenges will be described. Potential strategies/innovations for improving mental health care in hemodialysis will be identified and categorized according to the thematic analysis. Data will be reported in two parts:

1. Description of mental health care needs and potential strategies/innovation priorities for each innovation area
2. Set of themes that elucidate the reasons why the groups have chosen priorities

Data collected from all Canadian sites will be analyzed and reported in aggregate and by geographic region.

*STATUS: Data collection completed (Sept 2024). Data Analysis is nearing completion.*

## **2) PRIORITY SETTING PROCESS WORKSHOP (PSP):**

Data gathered from the surveys will be used to develop and guide the PSP workshop. Multiple stakeholders will be identified and invited to participate in the PSP workshop.

Patients and caregivers with direct facility-based hemodialysis experience will be recruited from across Canada (Vancouver, Calgary, Edmonton, Winnipeg, Vancouver, Toronto, Ottawa, Montreal, Halifax). Each site will be asked to identify and suggest 5-6 in-centre people receiving hemodialysis and/or their caregivers that could participate in a two-day priority-setting workshop in Winnipeg. People receiving hemodialysis and their caregivers will be asked for verbal consent to contact by a nurse or other health care provider at their hemodialysis centre. If they consent to being contacted, the study research coordinator or research assistant will contact them in person (when possible)/ by phone or video conference (as per their preference) and provide them with the summary letter of information and invitation to participate. We expect to invite the following number of individuals:

- i. Two to three people receiving hemodialysis/caregiver participants from each site, including approximately 7 Indigenous individuals (minimum total n=25).
- ii. Nephrologists/site leads from sites participating in the survey (n=5)
- iii. Researchers familiar with administering the survey in participating hemodialysis units (n=5).
- iv. Nurses and other allied healthcare providers working in facility-based hemodialysis(n=6-10)
- v. an Indigenous Elder and Knowledge Keeper (n=2)
- vi. Policy-/decision-makers in hemodialysis from across Canada (n=6)

Participants in the workshop will generate the top challenges to mental health to address from a shortlist identified by the surveys. The research coordinator and research assistants will document the results and prioritizing as it occurs in real-time. With permission from the participants, notes, audio/video recording and photographs may be taken during the course of the PSP workshop.

Day 1 of the PSP workshop will generate the top priority challenges to mental health to address for individuals receiving hemodialysis utilizing a modified James Lind Alliance approach.

Day 2 of the PSP workshop will employ a modified Co-Design process to identify the strategies to best address mental health care needs of people receiving hemodialysis.

These results will inform Phase 2 of the research project in which we will develop, implement and evaluate optimal evidence-based mental health support strategies for Canadians on hemodialysis.

Due to the nature of the topic of mental health care, a mental health counsellor or therapist will be available to debrief with participants after (or if necessary, during) each day of the PSP workshop.

### **Survey and PSP Consent:**

Participants will be fully informed of the purpose of the research, that their participation is voluntary, that they may refuse to respond to any of the questions and that they may withdraw at any point in time. They will be asked to sign a consent form to participate in the focus groups or interviews, priority-setting process workshop this will be discussed with all participants prior to commencement. Participants will be offered the opportunity to ask their own questions and request additional information about the study by contacting the research team. Consent to participate in the survey will be implied by overt action (completion of the survey). Survey participants will not be asked to sign an informed consent form (waiver of consent).

***STATUS:** Completed. Workshop occurred June 7-9, 2024; manuscript in progress.*

**Aim 3: Design an evidence-based mental health support strategy tailored for Canadians receiving hemodialysis, and develop implementation and evaluation plans to test this strategy.**

### **Dialectical Behavioural Therapy**

Based on data gathered through the Mind the Gap surveys and the Priority Setting Workshop, we have identified the top 5 challenges to mental well-being in facility-based hemodialysis as: loss of control, lack of acceptance and/or adjustment to the situation, lack of trust and confidence in the healthcare system and providers, dialysis-related symptoms, and feeling overwhelmed. After discussions with various stakeholders, we reached consensus that implementation of a Dialectical Behavioural Therapy (DBT) program, which targets 4 key concepts: mindfulness, distress tolerance, emotional regulation, and interpersonal effectiveness, has potential to address most of these five challenges. DBT has been used in many different settings (treatment of borderline personality disorder, substance abuse, improving self-esteem in adolescents, improving corporate culture) and populations, but to our knowledge has not been studied in the hemodialysis population.

We will use a quasi-experimental pre/post study design to pilot two 12-week group DBT sessions in Manitoba that will be led by a licensed clinical psychologist who is trained and certified in delivery of DBT. Licensed clinical psychologist services will be provided by Tomfohr&Roos. Additional staff (e.g. Licensed Kidney Health Manitoba Social Worker at SOGH and/or a clinical psychology practicum student supervised by the licensed psychologist) may also co-facilitate the group depending on timing and human resources availability. An initial DBT group will meet in person at SOGH weekly for 12 weeks. Following completion of and incorporating feedback from the first session, a second virtual 12-week DBT group session will be implemented.

**Study Setting:**

Two 12-week DBT sessions (one virtual and one in-person) will be provided. The in-person sessions will be held weekly at the Seven Oaks General Hospital Campus in meeting rooms away from the hemodialysis unit. Virtual sessions will be video conferences held using the MS Teams platform.

**Study Population:***Inclusion Criteria:*

- Age  $\geq$  18 years old
- Individuals followed in the Manitoba Kidney Health Program at the SOGH or HSC sites with advanced chronic kidney disease not yet on facility-based hemodialysis but with plans to start within 1 month; OR
- Individuals followed in the Manitoba Kidney Health Program at the SOGH or HSC sites who have initiated facility-based hemodialysis within the last 90 days
- Able and willing to attend weekly DBT sessions (either virtually or in-person)
- Experiencing self-reported psychological distress related to advanced kidney disease or initiation of hemodialysis
- Deemed eligible to participate by study clinical psychologist

*Exclusion Criteria:*

- Unable to complete intervention due to planned relocation/transplant/modality change
- Unable to communicate in English
- Deemed by hemodialysis unit staff/physician/study psychologist to be unable to participate fully in study activities due to:
  - Actively participating in psychiatric care with psychiatric (DSM-5) diagnosis
  - Requiring referral for psychiatric care as per facility-based HD care provider assessment
  - Current psychotic symptoms
  - Cognitive impairment that would limit ability to participate in group or complete homework
  - Safety risk to staff (e.g. physical aggression)
  - Antisocial personality disorder or other issues that may limit ability to constructively participate in peer group
  - Severe comorbid substance use disorder (if present will offer referral to addictions resources or Addictions Psychiatry)

**Outcomes:*****Primary Outcome Feasibility measured by (collected at end of 12-week DBT session):***

a. *Recruitment:* Number of individuals recruited/Number of eligible individuals approached  $\geq$  30%

b. *Attendance:*

i. Mean Proportion of total DBT sessions attended  $\geq$  50%

- ii. Proportion of participants who attend all DBT sessions and complete all weekly homework sheets

*c. Study withdrawal:*

- i. Proportion of individuals who miss  $\geq 4$  DBT sessions in a row
- ii. Proportion of and reasons for study withdrawal

*d. Difference in recruitment and attendance rates between in-person and virtual DBT sessions*

**Secondary Outcomes:** measured by median change from pre-, to 6 weeks, and post-intervention (12 weeks):

All participants will complete:

a. **Anxiety symptoms** measured by the LEVEL 2 – Anxiety – Adult (PROMIS Emotional Distress – Anxiety - Short Form). This 7-item self-reported survey asks about the current severity/presence of the individual's anxiety over the past 7 days, using a 5-point Likert scale ranging from 1 (never) to 5 (always).

Time for completion: 5 minutes

b. **Resilience** measured using the two-item version of the Connor–Davidson Resilience Scale. This 2-item self-reported survey asks the individual to respond to the following statements: "I am able to adapt when changes occur" and "I tend to bounce back after illness, injury, or other hardships" using a 5-point Likert scale ranging from 0 (not true at all) to 4 (true nearly all of the time). Validated in multiple populations.

Time for completion: Less than 5 minutes

c. **Dialysis-related symptoms** using the Edmonton Symptom Assessment System Revised (ESAS-r). This 10-item self-reported survey asks about the current severity/presence of common symptoms experienced by people receiving hemodialysis over the past 7 days, using an 11-point Likert scale ranging from 0 to 10 (i.e.; for pain: 0 = no pain at all; 10 = worst pain possible).

Time for completion: 5 minutes

d. **Emotional Distress** using the self-reported National Comprehensive Cancer Network (NCCN) Distress Thermometer. This single-item measure asks the individual about their distress level experienced in the past 7 days, using a 10-point Likert scale ranging from 0 (no distress) to 10 (extreme distress). Additionally, there is a 39-item problem list used to identify potential sources of distress in individuals, categorized into five domains: physical, practical, social, emotional, and spiritual/religious.

Time for completion: 1-10 minutes.

e. **Well-being** using the PROMIS Neuro-QOL V1.0 Positive Affect and Well-Being Short Form. This 9-item self-reported survey measures positive aspects of mental health and well-being in the past week, using a 5-point Likert scale ranging from 1 (never) to 5 (always). Time for completion: 5 minutes

In addition, participants will complete a questionnaire seeking perspectives on participant experiences with the DBT program at the end of the 12 week DBT program.

f. **End of study participant questionnaire:** The initial version of this 10-item self-reported questionnaire investigating perspectives on participant experiences in the DBT groups will be piloted by study patient partners to ensure readability and face validity and modified accordingly. The survey includes questions that require yes/no and open text answers to provide participants with ample opportunity to provide and explain feedback regarding the DBT program. We will use perspectives shared through this questionnaire to modify the plans for the virtual DBT session and future in-person DBT groups.

Time for completion: 5-10 minutes

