### **Recruitment and Consent for DBT Groups:**

At SOGH, there are currently 160 individuals that start hemodialysis per year. For the purposes of this study, we will aim to recruit 15 individuals, to account for no shows and dropouts, for the in-person DBT group from the SOGH Hemodialysis Units and Multi Care Kidney Clinic. For the virtual DBT group, we will recruit 20 individuals from SOGH and HSC Hemodialysis Units and relevant Kidney Clinics.

Prior to the initiation of the DBT pilot intervention, [name] and the research coordinator will notify and orient healthcare staff to the study through an emailed letter of information and brief presentation to staff in the HD units and Kidney Clinics at both sites. An information poster advertising the DBT groups will be posted in the waiting room of Kidney Clinics and HD waiting rooms at both sites.

Potential recruits for the DBT groups will be screened for eligibility by a member of the individual's circle of care based on the inclusion criteria. If eligible, the individual's bedside or clinic nurse will approach them to briefly introduce the study and offer the potential recruit to opportunity be contacted by the study research coordinator for more information about the study by signing the Consent to Contact Form. This will then be returned to the study research coordinator. Participants will then be contacted by the study research coordinator (in person at hemodialysis/clinic or by phone call or email depending on the individual's preference) who will describe the study, the purpose of the research, the voluntary nature of participation and that participants may withdraw at any point in time and that the decision to participate or not will not impact their standard medical care. The coordinator will review the written consent form for the DBT intervention project with potential participants. Potential participants will be offered the opportunity to ask their own questions and request additional information about the study and will be given at least 24 hours to consider whether they want to participate or not. Consent to participate will be indicated through an individual's signature on the written consent form. All participants will read, sign, and date the consent form before undergoing any study procedures. A copy of the signed consent will be given to the participant. All original signed consents will be filed in a locked cabinet at CDIC.

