**Table 2: Study Schedule**

SCHEDULED STUDY PROCEDURE	SCREEN AND ENROLLMENT (VISIT 0)	BASELINE (VISIT 1)	MID INTERVENTION 6 WEEKS (VISIT 2)	FINAL VISIT 12 WEEKS (VISIT 3)
HCP INCLUSION / EXCLUSION	X			
CONSENT TO CONTACT	X			
INFORMED CONSENT	X			
FINAL STUDY ELIGIBILITY	X			
DEMOGRAPHIC DATA		X		
MEDICAL HISTORY		X		
CONCOMITANT MEDICATIONS		X		X
LAB DATA		X		X

PRIMARY FEASIBILITY DATA				
NUMBER APPROACHED				X
NUMBER ELIGIBLE				X
SESSION ATTENDANCE				X
STUDY WITHDRAWAL				X
SECONDARY OUTCOMES				
LEVEL 2 –ANXIETY – ADULT (PROMIS EMOTIONAL DISTRESS – ANXIETY – SHORT FORM)		X	X	X
CONNOR-DAVIDSON RESILIENCE SCALE (2-ITEM)		X	X	X
EDMONTON SYMPTOM ASSESSMENT SYSTEM REVISED (ESAS-r)		X	X	X
NATIONAL COMPREHENSIVE CANCER NETWORK (NCCN) DISTRESS THERMOMETER		X	X	X
PROMIS NEURO-QOL V1.0 POSITIVE AFFECT AND WELL-BEING SHORT FORM		X	X	X
LEVEL 2 – ANGER – ADULT (PROMIS EMOTIONAL DISTRESS – ANGER – SHORT FORM)		X	X	X
PROMIS V1.1– PAIN INTERFERENCE 6a SHORT FORM		X	X	X
LEVEL 2 – SLEEP DISTURBANCE – ADULT (PROMIS SLEEP DISTURBANCE – SHORT FORM)		X	X	X
END OF STUDY PARTICIPANT QUESTIONNAIRE				X

*Focus groups will now occur following the DBT pilot intervention if the intervention demonstrates feasibility, rather than after the above two activities as indicated in previous version of the protocol.*

**3) FOCUS GROUPS : *Collect additional perspectives regarding tailoring of DBT intervention and potential barriers/facilitators to implementation – WILL BE COMPLETED AFTER AIM 3 ONLY IF PILOT DBT INTERVENTION DEMONSTRATES FEASIBILITY***

Focus groups and interviews will help us gain deeper perspective and understanding as to how the DBT intervention should be tailored for people receiving HD with diverse characteristics and help identify potential barriers/facilitators to its implementation. Stakeholders will include healthcare providers, people receiving HD, caregivers, Indigenous consultants, researchers and policy-/decision-makers.

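### The primary recruitment rate counts only eligible people, but eligibility includes willingness to attend and no step is named at which it is fixed, so people who decline can fall out of the denominator

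*Protocol*

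**What the plan says.** In the Protocol's Outcomes section, recruitment is the first primary feasibility measure: "Number of individuals recruited/Number of eligible individuals approached", to be at least 30%.

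The inclusion criteria under Study Population contain two items that bear on who counts as eligible: "Able and willing to attend weekly DBT sessions (either virtually or in-person" (the closing bracket follows in the text) and "Deemed eligible to participate by study clinical psychologist".

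Recruitment and Consent for DBT Groups gives the sequence. Potential recruits are "screened for eligibility by a member of the individual's circle of care based on the inclusion criteria". Then: "If eligible, the individual's bedside or clinic nurse will approach them to briefly introduce the study". A person who is interested agrees to be contacted "by signing the Consent to Contact Form. This will then be returned to the study research coordinator".

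Table 2 schedules the number approached and the number eligible as feasibility data. At the screening visit it lists an inclusion and exclusion check by the healthcare provider and, further down and below informed consent, a separate final eligibility decision.

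The focus groups go ahead only if the pilot shows feasibility.

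**The concern.** A recruitment rate in a feasibility pilot should show what share of the people for whom the programme is meant will take it up when offered. Willingness to attend is therefore what the rate should measure. Here it also helps decide who enters the denominator. If the criterion is applied as written, an unwilling person is not an eligible person, and their refusal does not count against the programme.

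Recruitment is one of only two feasibility measures with a numeric bar; the other is mean attendance of at least 50%. The feasibility verdict decides whether the focus groups happen. The same rate also feeds the last primary item, the difference in recruitment between the in-person and virtual groups. If the two groups handled decliners differently, that difference could reflect counting practice and not uptake.

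**Working it through.** **Which decision defines eligible?** Set side by side, the sections allow two readings.

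- *Pre-approach screen.* Staff screen, then the nurse approaches those who pass. Someone who passes and then declines was both eligible and approached, and stays in the denominator.
- *Final eligibility.* The screen is said to rest on the inclusion criteria, but willingness can be learned only from the person, and the psychologist's judgement would ordinarily need contact too. Table 2 has a later, final decision. If that one counts, the denominator shrinks towards those who consent.

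The Outcomes section does not choose between them.

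**Can refusals be counted?** The number approached is a scheduled item. The nurse makes the first approach, and the only paper described as going back to the coordinator is a signed form from someone who agreed to contact. The Data Management section speaks of data for people enrolled. No form or log is described for a refusal made to the nurse.

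**The plan's own figure.** The 30% bar comes with no derivation, so there is nothing to reproduce. What can be computed is what it requires. The recruitment targets are 15 (in-person) and 20 (virtual), 35 in all. The largest denominator that still passes is the target divided by 0.30, rounded down:

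- 15 / 0.30 = 50
- 20 / 0.30 = 66.7, so 66
- 35 / 0.30 = 116.7, so 116

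**Effect of losing decliners.** Let R be the number recruited, A the number approached, and f the share of non-recruited people left out of the denominator. For simplicity all A − R non-recruited people are taken to be decliners.

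Apparent rate = R / (A − f(A − R)).

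Setting this to 0.30 with true uptake p = R/A gives the share that must be left out for the bar to be reached:

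f = (1 − p/0.30) / (1 − p).

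The protocol gives neither p nor f, so both are assumptions. For R = 15:

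| True uptake p | Approached A | Decliners A − R | To leave out to reach 15/50 | f |
|---|---|---|---|---|
| 25% | 60 | 45 | 10 | 22% |
| 20% | 75 | 60 | 25 | 42% |
| 15% | 100 | 85 | 50 | 59% |
| 10% | 150 | 135 | 100 | 74% |

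The formula for f does not depend on R, so the shares are the same for 20 or 35 recruits, apart from rounding to whole people.

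Some apparent rates:

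- p = 20%, f = 0.50: 15 / (75 − 30) = 15/45 = 33.3%, a pass.
- p = 15%, f = 0.50: 15 / (100 − 42.5) = 15/57.5 = 26.1%, still a fail.
- p = 15%, f = 0.75: 15 / (100 − 63.75) = 15/36.25 = 41.4%, a pass.
- p = 10%, f = 0.75: 15 / (150 − 101.25) = 15/48.75 = 30.8%, a pass.
- f = 1, any p: R/R = 100%.
- f = 0: the rate equals p, and 10% to 25% uptake fails.

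**The case against.** The strongest reply is that the recruitment section screens first and approaches second, so those who decline after passing the screen remain eligible and approached. On that reading 30% is a real test. This is a fair reading and may be what was meant. It is not secured by the text, because willingness is among the criteria the screen is said to apply and a later eligibility decision exists.

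A reader might infer more than the protocol supports on four points:

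- *That the bar is passed by construction.* This holds only if every decliner is classed as ineligible. Otherwise it takes a loss of roughly a fifth to three quarters of decliners, depending on true uptake.
- *That people who refuse at the nurse stage leave no record.* Table 2 schedules a count of people approached. What is missing is a described way to obtain it, and a screening log may exist outside the protocol.
- *That placing the two counts in the 12-week column means counting starts too late.* Attendance and withdrawal stand in the same column and plainly build up over the programme. The column fits the time at which totals are compiled.
- *That the posters let self-referred people into the numerator without an approach.* The protocol mentions posters but describes no such route to enrolment.

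It is also right that a denominator including people excluded on clinical grounds would over-correct, since the group is not meant for them.

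Finally, this is a small pilot with descriptive feasibility outcomes, recruitment is one of several components, and a statistical analysis plan could still define the denominator. That limits the weight of the point. But a later definition may not be able to recover refusals that nobody logged.

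**Conclusion.** The point holds as an ambiguity in a primary outcome that has a threshold, with a bias in a known direction if the criteria are applied as written. One reading returns the true uptake; the other returns a rate that rises towards 100% as decliners are reclassified as ineligible. Near the bar a modest loss is enough: at a true uptake of 25%, leaving out 10 of 45 decliners turns a fail into a pass. At 10% it takes 100 of 135.

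These sizes rest on assumed uptake and assumed losses and on treating all non-recruited people as decliners. The protocol does not show that any such loss will occur. It does leave the rate without a single determinable value, and it describes no route for the refusals that the rate needs. Because the feasibility verdict governs the focus groups, this should be settled before recruitment, or as early in it as possible.

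**What to change.** 1. In the Outcomes section, define the denominator as everyone approached who meets the pre-approach criteria other than willingness or ability to attend, with the clinical exclusions kept. State that those who refuse contact, decline consent, or say they cannot or will not attend remain in it.
2. Keep willingness to attend as a condition of enrolment only.
3. Have the nurses keep an anonymous tally of approaches and refusals during recruitment, with the reason where one is offered, and pass it to the coordinator as the source for the number approached.
4. Report the cascade from approached to enrolled for each group, with people screened out by the psychologist on a separate line.

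The cost is a few sentences of protocol wording and a short tally for clinic and unit nurses. The observed rate will probably look less favourable than one computed among willing people.
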